### 6.3.3 Overall Eczema Area and Severity Index Score

Overall Eczema Area and Severity Index (EASI) total score is the sum of the scores for 4 body regions (face, neck, and head; upper limbs; trunk; and lower limbs). The score for each region will be calculated as shown in Table 6.3-2.

Table 6.3-2 EASI Score for Each Region	
Body region	Calculation of the score for each region
Face, neck, and head	$(E+I+Ex+L) \times \text{score of affected BSA} \times 0.1$
Upper limbs	$(E+I+Ex+L) \times \text{score of affected BSA} \times 0.2$
Trunk	$(E+I+Ex+L) \times \text{score of affected BSA} \times 0.3$
Lower limbs	$(E+I+Ex+L) \times \text{score of affected BSA} \times 0.4$

- E = severity score of erythema; I = severity score of infiltration/papules; Ex = severity score of excoriation; L = severity score of lichenification
- Severity score: clear = 0; slight = 0.5; mild = 1; mild-moderate = 1.5; moderate = 2; severe = 2.5; very severe = 3
- Score of BSA: clear = 0; 1% to 9% = 1; 10% to 29% = 2; 30% to 49% = 3; 50% to 69% = 4; 70% to 89% = 5; 90% to 100% = 6

### 6.3.4 EASI Symptom Score

Each EASI symptom score (erythema, infiltration/papules, excoriation, and lichenification) will be determined as the sum of the severity scores (Body Regions Scores) for 4 regions (face, neck, and head; upper limbs; trunk; and lower limbs) (The scores of affected BSA or multipliers will not be used in the calculation).

## 6.4 Study Week Windows

The definitions of timepoints for analysis are described in Table 6.4-1 and Table 6.4-2. Timepoints, including unscheduled visits and visit at discontinuation, will be determined based on the number of days from the start of IMP administration. However, for Verbal Rating Scale (VRS), the timepoint will be determined based on the amount of time that has elapsed from the start of IMP administration. For efficacy variables, the data obtained between the day of the start of IMP administration and 7 days after the last IMP administration will be used in analyses. If multiple data exist within the allowable window of the timepoint, the data obtained last will be used for analyses. Data for the Last Visit will be defined as the last data obtained between the day of the start of IMP administration and 7 days after the last IMP administration (including data obtained at discontinuation) for efficacy variables or as the last data obtained after the start of the IMP administration for safety variables.

In analyses, baseline data will be defined as data obtained on the day or at the date and time before and nearest to the start of IMP administration, including the screening data.

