6.1 Dose, Regimen, and Treatment Period

The 0.3% or 1% formulation or the vehicle of OPA-15406 ointment will be administered twice daily (approximately 12 hours apart between morning and night administration) for 8 weeks.

The amount of IMP (g) per dose is calculated as follows.

- 1) The subject's BSA (m^2) will be calculated based on height and body weight at the screening examination, using the following equation.

$$\text{BSA (m}^2\text{)} = \sqrt{\frac{\text{Ht (cm)} \times \text{Wt (kg)}}{3600}}$$

BSA = body surface area;
Ht = height; Wt = body weight
(Mosteller 1987)⁴

- 2) Based on the subject's BSA (m²), the amount of administration (g) for 1% of BSA will be selected from [Table 6.1-1](#).
- 3) The treatment area will be specified (see [6.2 "Treatment Area"](#)).
- 4) The amount of IMP (g) per dose will be calculated as "the amount of administration for 1% of BSA (g)" × "treatment area (%)."

Table 6.1-1 Amount of Administration (g) for 1% of BSA Based on the Subjects' BSA (m²)					
BSA (m²)	<1.0	≥1.0 and <1.3	≥1.3 and <1.6	≥1.6 and <1.9	≥1.9
Amount of administration (g) for 1% of BSA	0.1	0.15	0.2	0.25	0.3

[Rationale for dose, regimen, and treatment period]

[Regimen]

Skin preparations are always exposed to opportunities of being removed after administration to the skin, such opportunities as washing the face, bathing, adhesion to clothing, or sweating resulting in dilution. To be sure that effective concentration on the skin is maintained, it is desirable that the IMP be administered multiple times a day. In consideration of the fact that people generally wash their face and hands after getting up and when bathing at night, twice daily administration is considered highly convenient for patients, and it may contribute to achieving the best adherence. Therefore, twice-daily administration is employed.

[Dose]

In the phase 1 trial in AD patients in the US (271-12-204), the efficacy of OPA-15406 was suggested in the 0.3% and 1% formulations out of the 0.3%, 1%, and 3% formulations tested. In the phase 2 trial outside Japan (271-12-205), the efficacy of OPA-15406 was investigated by selecting the 0.3% and 1% formulations. The results showed that the 1% formulation had a significantly higher efficacy in the primary efficacy endpoint compared to the vehicle, and the 0.3% formulation also had a higher efficacy compared to the vehicle. For this trial, the concentrations of 0.3%

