7.1.5 Allocation of Investigational Medicinal Products to Subjects

The investigator or subinvestigator will enter the necessary information for the subject's eligibility in the IWRS. On the day of the baseline examination, the subjects confirmed to be registered in the IWRS will be allocated to the 0.3% OPA-15406 group, the 1% OPA-15406 group, or the vehicle group. The investigator or subinvestigator will confirm the allocation result and the amount of IMP to be prescribed for 2 weeks on the IWRS screen displaying the registration result, and prescribe the IMP. The weight of the dispensed IMP will be measured (unit in g; rounded to the one decimal place; same method for all subsequent IMP weight measurements hereinafter) The IMP administration will be started at the trial site after all baseline examinations are finished, and the time and date of administration will be recorded. The subjects will be instructed to visit the trial site without morning IMP administration on the day of their next visit.

**7.1.6 Baseline Examination (2 Hours, 4 Hours, and 8 Hours Postdose):
To be Conducted at Specific Trial Sites**

Application will be started within the trial site after all the baseline examinations are finished, and the source document and CRF will be recorded accordingly.

- Blood sampling for plasma drug concentration

7.1.7 Between the Day of Baseline Examination and the Day of Week 1 Examination

The investigator or subinvestigator will instruct the subject to evaluate the following item at 4 ± 2 hours, 8 ± 2 hours, and 12 ± 2 hours (if possible) after the first IMP administration on the day of the baseline examination, and then twice daily from the next day (before IMP administration in the morning and at night) up to the morning of the Week 1 examination (before administration) (up to the morning of Day 7 at the latest).

- VRS for pruritus

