 - a) Change from baseline in the total score of EASI and each symptom score at Week 1, Week 4, and Week 8
 - b) Change from baseline in VAS for pruritus at Week 1, Week 4, and Week 8
 - c) Change from baseline in the total score of DLQI at Week 1, Week 4, and Week 8
 - d) Change from baseline in the total score of POEM at Week 1, Week 4, and Week 8
 - e) Change from baseline in the total affected BSA (%) at Week 1, Week 4, and Week 8
- Change from baseline in VRS for pruritus up to Day 7
Using the OC and LOCF data sets up to Day 7, the analysis of covariance (ANCOVA) with treatment (0.3% OPA-15406, 1% OPA-15406, or vehicle) and baseline values as factors will be applied to the change from the baseline at the respective timepoints as a response variable. The least square mean will be calculated by treatment group and timepoint. Also, the difference in the least square means between the vehicle group and the respective OPA-15406 groups, the two-sided 95% confidence interval, and the p value will be calculated. Using the OC and LOCF data sets, the descriptive statistics will be calculated for measured values and changes from the baseline at the respective timepoints by treatment group and timepoint. Assessments will be made at 4, 8, and 12 hours after the start of administration, 1 day after the start of administration (morning and night), and thereafter in the same manner up to Day 7 (morning).
- Time to response in IGA and VRS
For time to response in IGA and VRS, Kaplan-Meier plots will be generated for each treatment group and vehicle group. For IGA, subjects with an IGA score of 0 (clear) or 1 (almost clear) with an improvement by at least 2 grades from the baseline are defined as responders. For VRS, subjects with VRS score of 0 (none) or 1 (mild) with an improvement by at least 1 grade from the baseline are defined as responders.

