**Table 6.4-2 Timepoints and Allowable Windows for VRS**

Timepoint	Allowable Window (Hours After the Start of IMP Administration)		
Hour 4	1	-	< 6
Hour 8	6	-	< 10
Hour 12	10	-	< 18
Hour 24	18	-	< 30
Hour 36	30	-	< 42
Hour 48	42	-	< 54
Hour 60	54	-	< 66
Hour 72	66	-	< 78
Hour 84	78	-	< 90
Hour 96	90	-	< 102
Hour 108	102	-	< 114
Hour 120	114	-	< 126
Hour 132	126	-	< 138
Hour 144	138	-	< 150
Hour 156	150	-	< 162
Hour 168	162	-	< 174

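### Elapsed-time VRS windows with a last-reading rule can discard scheduled pruritus readings and mix morning with night readings in CT-5.7.1 to CT-5.7.3

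*SAP*

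**What the plan says.** **Collection.** Protocol 7.1.7 asks for VRS at 4, 8 and (if possible) 12 h after the first application, each with a margin of 2 h, "and then twice daily from the next day (before IMP administration in the morning and at night"), ending "up to the morning of Day 7 at the latest". Protocol 6.1 puts the two daily applications "approximately 12 hours apart between morning and night administration". No clock time is set for the first one. Protocol 7.1.5 says only: "The IMP administration will be started at the trial site after all baseline examinations are finished".

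**Protocol timepoints.** Protocol 11.3.1.2 lists the 4, 8 and 12 h assessments, then "1 day after the start of administration (morning and night), and thereafter in the same manner up to Day 7 (morning"). SAP 9.2.5 repeats these slots.

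**Assignment in the SAP.** Under SAP 6.4, "the timepoint will be determined based on the amount of time that has elapsed from the start of IMP administration". Table 6.4-2 ("Timepoints and Allowable Windows for VRS") makes Hour 12 run from 10 to <18 h. From Hour 24 to Hour 168 it sets adjoining 12 h windows, each from 6 h before to 6 h after the nominal hour. SAP 6.4 adds: "If multiple data exist within the allowable window of the timepoint, the data obtained last will be used for analyses".

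**Second VRS analysis.** SAP 9.2.5 also plans the analysis separately for morning and evening, using the CRF time label and expressly not Table 6.4-2. These are CT-5.7.4 and CT-5.7.5. SAP 13.1 does not list the elapsed-time windows as a change from the protocol.

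**The concern.** The readings follow the subject's day, but the windows follow the hour of the first dose. A 12 h window is sure to hold one reading only if readings are exactly 12 h apart, which the protocol does not require. When two fall in one window, the last-reading rule removes a scheduled reading that was taken on time, and another window is left empty.

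A second effect does not depend on the spacing. Subjects whose first dose comes late relative to their morning reading have every reading shifted down one window. A single nominal hour then combines morning itch for some subjects with night itch for others, and the next morning's reading competes with the 12 h reading.

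What is at stake is precision at alternate timepoints and a clear time course in CT-5.7.1 (MMRM), CT-5.7.2 (ANCOVA, OC) and CT-5.7.3 (ANCOVA, LOCF). In the LOCF table an empty window is filled with an earlier value although a later reading was collected.

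**Working it through.** **Inputs.** The windows are those of Table 6.4-2, with the last-reading rule of SAP 6.4. Let *m* and *n* be the clock times of the morning and night readings and *S* that of the first dose. The documents give none of these three, so all values below are assumptions. Twice-daily readings run over mornings k = 1 to 7 and nights k = 1 to 6, which is 13 readings and matches the 13 windows from Hour 24 to Hour 168.

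**Elapsed time.** Morning k falls at 24k + m − S hours and night k at 24k + n − S hours. From Hour 24, window boundaries lie at 18, 30, 42, … h.

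**When two readings collide.**
- Daytime gap n − m above 12 h: a night and the next morning share a window when m + 6 < S ≤ n − 6, and the night reading is lost.
- Gap below 12 h: a morning and the same night share a window when n − 6 < S ≤ m + 6, and the morning reading is lost.
- In both cases the band of first-dose times is as wide as the gap's departure from 12 h.

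**Example.** Diary 07:00/21:00, S = 14:00.
- First night: 24 + 21 − 14 = 31 h. Following morning: 48 + 7 − 14 = 41 h. Both lie in Hour 36 (30 to <42), so the 31 h reading is dropped.
- This repeats at Hours 60, 84, 108, 132 and 156, so 6 of 13 readings are lost, all of them night readings.
- The first morning is at 24 + 7 − 14 = 17 h, in Hour 12. The seventh is at 168 + 7 − 14 = 161 h, in Hour 156. Hours 24, 48, 72, 96, 120, 144 and 168 are empty.
- The band is 13:00 < S ≤ 15:00. For 08:00/19:00 it is 13:00 < S ≤ 14:00, and mornings are lost instead.

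**Exact 12 h gap (08:00/20:00).** No two twice-daily readings collide, but two effects remain when S > m + 6 = 14:00.
- With S = 15:00 the next morning is at 24 + 8 − 15 = 17 h, in Hour 12. A 12 h reading (10 to 14 h) lies in the same window and is displaced if it was taken.
- With S = 15:00, Hour 36 holds a morning reading (48 + 8 − 15 = 41 h). With S = 11:00 it holds a night reading (24 + 20 − 11 = 33 h). For first doses spread evenly over 10:00 to 16:00, the late share is 2/6 = 33%.

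**Frequency, fixed gap of 12 h ± d.** With first doses spread evenly over 6 h containing the band, the share affected is d/6 and the mean loss is (d/6) × (6/13) = d/13.
- d = 0.5 h: 8% of subjects, 4% mean loss.
- d = 1 h: 17% and 8%.
- d = 2 h: 33% and 15%.

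**Frequency, simulated diaries.** 40,000 subjects per scenario, uniform clock times, mornings 06:30–08:00, first dose 10:00–16:00:

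| Night readings | Mean gap | Mean loss | Lose ≥5 of 13 (fixed times / redrawn daily) | Empty at Hours 24, 48, … 144 | OC standard error |
|---|---|---|---|---|---|
| 19:00–20:30 | 12.5 h | 5% | 11% / 1% | 9% | +5% |
| 20:00–22:00 | 13.75 h | 13% | 29% / 17% | 29% | +19% |
| 21:00–23:00 | 14.75 h | 19% | 42% / 33% | 42% | +31% |

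The OC column is 1/√(1 − share empty): 1/√0.91 = 1.05, 1/√0.71 = 1.19, 1/√0.58 = 1.31. In the MMRM the rise is about 1–3%, 4–12% and 8–20%, for an assumed within-subject correlation of 0.5 to 0.8. With first doses over 09:00–17:00 the mean losses are 4%, 10% and 16%.

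First doses before noon lose nothing in these scenarios, because m + 6 is never earlier than 12:30. With unbounded day-to-day variation around 07:30/19:30, first doses from 09:00 to 12:00 lose 0.0% of readings at a standard deviation of 0.5 h, 0.8% at 1 h and 3.5% at 1.5 h.

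**The case against.** The strongest reply is that the larger figures rest on diaries that fit the protocol poorly. Spacing of about 12 h is specified, while the worked example uses 14 h and two of the three scenarios average 13.75 and 14.75 h. Nothing shows that afternoon first doses are common, and at the pharmacokinetic sites sampling to 8 h after dosing makes them unlikely. This stands: the 12.5 h row is the one to quote.

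Thirteen readings is also a maximum. The diary stops on the morning of the Week 1 visit, which may be two days early, so late windows such as Hour 168 can be empty under any rule. That stands too.

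Mixing clock times is inherent in an elapsed-time analysis, and SAP 9.2.5 already provides an analysis by time of day. This answers much of the mixing point. It does not justify discarding readings, and the output list has no label-based counterpart to the LOCF table: CT-5.7.4 is MMRM and CT-5.7.5 is OC.

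The documents do not support four stronger readings that a reader might infer:
- **The VRS comparison is biased.** First-dose time is not tied to arm.
- **Night readings are routinely lost.** Loss requires a first dose inside a limited band.
- **Exact 12 h spacing makes the windows safe.** The 12 h reading can still be displaced.
- **The day labels conflict.** The pharmacokinetic section calls the first-dose day Day 1, which would leave 11 twice-daily readings. But the VRS text counts from one day after the start, and Hour 168 is seven days after the first dose, so the VRS passages agree with each other.

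**Conclusion.** The defect is real and minor. The rule can drop scheduled readings whenever consecutive readings are less than 12 h apart and no window boundary falls between them. Separately, a first dose more than 6 h after the morning reading time can displace the 12 h reading and make Hour 36 a morning value for some subjects and a night value for others.

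Under the assumption closest to the protocol (mean gap 12.5 h, first doses 10:00 to 16:00), about 5% of twice-daily readings are lost and the OC standard error rises by about 5% at alternate timepoints. Losses of 13% and 19% need mean gaps of 13.75 and 14.75 h. All frequencies depend on assumed clock times.

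Among the VRS change-from-baseline tables only CT-5.7.1 to CT-5.7.3 are affected. VRS is a secondary endpoint, SAP 6.6.1 gives its p-values for reference, no between-arm bias is expected, and the primary IGA analysis is untouched.

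**What to change.** In SAP 6.4 and Table 6.4-2, keep the elapsed-time windows for the 4, 8 and 12 h readings only, so that the next morning's reading cannot replace a 12 h reading. A 12 h reading taken after midnight stays a 12 h reading. From the next calendar day, assign each reading to its morning and night slot by diary date and the CRF time label that SAP 9.2.5 already uses. State that the first such slot is the morning of the day after the first dose. Record the rule in SAP 13.1 wherever it differs from the protocol.

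The cost is a table edit and a small programming change, with no new data. The downside is that a slot no longer stands for a fixed number of hours since the first dose: 07:00 the next morning is 21 h after a 10:00 dose but 16 h after a 15:00 dose.

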**Table 6.4-1 Timepoints and Allowable Windows for Efficacy Variables (Except VRS) and Safety Variables**

Timepoint	Study Day	Allowable Window (Days After the Start of IMP Administration)		
Week 1	8	1	-	10
Week 2	15	11	-	21
Week 4	29	22	-	35
Week 6	43	36	-	48
Week 8	57	49	-	73

**Table 6.4-2 Timepoints and Allowable Windows for VRS**

Timepoint	Allowable Window (Hours After the Start of IMP Administration)		
Hour 4	1	-	< 6
Hour 8	6	-	< 10
Hour 12	10	-	< 18
Hour 24	18	-	< 30
Hour 36	30	-	< 42
Hour 48	42	-	< 54
Hour 60	54	-	< 66
Hour 72	66	-	< 78
Hour 84	78	-	< 90
Hour 96	90	-	< 102
Hour 108	102	-	< 114
Hour 120	114	-	< 126
Hour 132	126	-	< 138
Hour 144	138	-	< 150
Hour 156	150	-	< 162
Hour 168	162	-	< 174

## 6.5 Handling of Missing Values

Missing data for incidence of success in IGA, the primary endpoint, will be handled as described in “[Section 6.3.1 Response in Investigator’s Global Assessment](#).” Other variables at each timepoint will be analyzed based on the OC and LOCF data sets.

## 6.6 Significance Level and Confidence Coefficient

The two-sided significance level is 5% with a two-sided 95% confidence interval.

### **6.6.1      Multiple Comparisons and Multiplicity**

For the primary analysis of incidence of success in IGA, the primary endpoint, a comparison will be performed between the vehicle group and 1% OPA-15406 group and between the vehicle group and the 0.3% OPA-15406 group. The closed testing procedure will be employed to avoid issue of multiplicity. When superiority of the 1% OPA-15406 group compared to the vehicle group is demonstrated with a two-sided significance level of 0.05, a comparison between the vehicle group and the 0.3% OPA-15406 group will be performed.

For variables other than the primary variable, p-values will also be computed for a reference indication of differences between the treatment groups. The multiplicity adjustment will not be conducted.

## **7      Disposition of Subjects**

### **7.1      Disposition of Subjects**

Data will be summarized for the overall population and by age group (<18 or  $\geq 18$ ). The numbers of screened and randomized subjects will be provided. The following frequency distributions will be provided for overall population and by treatment group, unless otherwise specified. The frequency distribution (number and percentage relative to all subjects randomized) of subjects treated, those who completed the trial, and those who discontinued the trial will be calculated. For subjects who discontinue the trial, the frequency distribution will be calculated by reason for discontinuation.

### **7.2      Statistical Analysis Sets**

Data will be summarized for the overall population and by age group (<18 or  $\geq 18$ ). For the randomized subjects, the number and percentage of subjects included in the FAS, SS, and pharmacokinetic analysis set will be provided.

### **7.3      Protocol Deviations**

The number and percentage of subjects with major protocol deviations will be provided for the overall population and by treatment group. The number and percentage of major protocol deviations occurring in each trial site will be provided for the overall population and by treatment group.

## **8 Description of Analysis Dataset**

### **8.1 Demographics and Baseline Characteristics**

Data will be summarized for the overall population and by age group (<18 or  $\geq 18$ ). For the randomized subjects, age, gender, duration of AD, body weight, height, BMI, race, baseline IGA score, and nation will be summarized for overall population and by treatment group using descriptive statistics or frequency distribution.

Affected BSA at baseline will be categorized as follows and summarized for overall population and by treatment group using frequency distribution.

Affected BSA categories:  $\geq 5\%$  to <10%,  $\geq 10\%$  to <30%, and  $\geq 30\%$

### **8.2 Medical History/Complications**

Medical history and complications will be coded by MedDRA/J system organ class (SOC) and preferred term (PT). The medical history and complications will be listed, but not summarized.

### **8.3 Prior and Concomitant Medications**

For the randomized subjects, the numbers and percentages of subjects who take any concomitant medication before the start of IMP administration, during the treatment period, and after the last IMP administration will be provided by medication for the overall population and by treatment group. The medications will be coded using the WHO Drug Dictionary, and summarized by ATC Classification Level 2 and Preferred Name.

### **8.4 Concomitant Therapies**

The concomitant therapies will be listed, but not summarized.

## **9 Efficacy Analyses**

Efficacy analyses will be conducted in the FAS.

## 9.1 Primary Endpoint

The primary endpoint is incidence of success in IGA at Week 4.

Comparisons of incidences of success in IGA at Week 4 between the 1% OPA-15406 group and the vehicle group, and between the 0.3% OPA-15406 group and the vehicle group will be conducted using the Cochran-Mantel-Haenszel test stratified by baseline IGA score (mild or moderate). The closed testing procedure will be employed to avoid issue of multiplicity. When superiority of the 1% OPA-15406 group compared to the vehicle group is demonstrated with a two-sided significance level of 0.05, a comparison between the vehicle group and the 0.3% OPA-15406 group will be performed. The difference in incidence of success in IGA between each OPA-15406 group and the vehicle group and its two-sided 95% confidence interval (a Mantel-Haenszel estimator of the common risk difference and its two-sided 95% confidence interval) will be computed. Additionally, two-sided 95% confidence interval for the incidence of success in IGA in each treatment group will also be calculated using Clopper-Pearson method.

The SAS code to compare the incidence of success in IGA by the Cochran-Mantel-Haenszel test and to calculate the difference in incidence of success in IGA and its two-sided 95% confidence interval is shown below.

```
proc freq ;
  tables BaselineIGA *Treatment*Response/riskdiff(common) cmh ;
  run;
```

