1.2.2.4 Phase 2 Trial in AD Patients Outside Japan (271-12-205)

In the phase 2 trial in AD patients (aged 10-70 years old) outside Japan, the efficacy, safety, and pharmacokinetics of the 8-week twice-daily multiple doses of OPA-15406 ointment was investigated by selecting 0.3% and 1% formulations (40 subjects for each group) for which the efficacy was suggested in the phase 1 trial in the US. The primary efficacy endpoint was established as the incidence of success in IGA (percentage of subjects with IGA score of 0 or 1 with improvement by at least 2 grades) at Week 4, and the incidence of success in IGA was 14.63%, 20.93%, and 2.70% in the 0.3% OPA-15406 group, the 1% OPA-15406 group, and the vehicle group, respectively. The 0.3% OPA-15406 group showed a higher incidence of success in IGA than in the vehicle group; however, no significant difference was observed between the groups ($p = 0.0690$, CMH test). In the 1% OPA-15406 group, a significant difference was observed in the incidence of success in IGA compared to the vehicle group ($p = 0.0165$, CMH test). Discontinuations due to adverse events occurred with 4 subjects (9.8%), 3 subjects (7.0%), and 7 subjects (18.9%) in the 0.3% OPA-15406 group, the 1% OPA-15406 group, and the vehicle group, respectively. Serious adverse events were reported as liver function test abnormal and multiple sclerosis in 1 subject each in the 0.3% OPA-15406 group, and giardiasis and depression in 1 subject each in the 1% OPA-15406 group; however, all of these events were determined as not IMP-related. In the results of clinical laboratory tests, vital signs, and 12-lead ECG, no marked difference was observed among the 3 groups. The plasma OPA-15406 concentrations at 4 hours post-administration at Week 4 were 0.236 to 7.26 ng/mL in 5 subjects in the 0.3% OPA-15406 group and 0.469 to 1.22 ng/mL in 4 subjects in the 1% OPA-15406 group.

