## 9.2 Secondary Endpoints

### 9.2.1 Incidence of Success in IGA at Week 1 and Week 8

Incidence of success in IGA at Week 1 and Week 8 (as well as Week 2 and Week 6) will be analyzed in the same manner as described in [Section 9.1](#).

The change in incidence of success in IGA (the incidence of success in IGA in the primary analysis and the incidence of success in IGA defining responders as subjects with an improvement in IGA to 0 [clear] or 1 [almost clear]) will be plotted by timepoint for each treatment group.

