## **9.5 Subgroup Analysis**

Incidence of success in IGA will also be analyzed in the following subgroups in the same manner as described in [Section 9.1](#).

Age: <18 or  $\geq 18$  years old

Gender: Male or female

Baseline IGA score: 2 (mild) or 3 (moderate)

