### 12.2 Rationale for the Number of Subjects

In the phase 2 trial outside Japan (271-12-205), the primary variable of incidence of success in IGA was 20.93% in the 1% OPA-15406 group and 2.70% in the vehicle group, respectively. In the present trial, with the assumption that the difference in incidence of success in IGA between the 1% OPA-15406 group and the vehicle group is similar to that obtained in the foreign trial, a sample size of 54 subjects per group at a two-tailed 5% level of significance was calculated with at least an 80% power. In consideration of possible discontinuations and dropouts, the number of subjects is established as 60 subjects per group.

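### The planned 95% interval for the difference in IGA success does not invert the CMH test and can be too narrow when responders are very few; a stratified score interval is a cheap improvement

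*SAP*

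**What the plan says.** SAP 9.1 compares each active arm with vehicle by a CMH test stratified on baseline IGA, 1% first and then 0.3% if the first comparison succeeds. For the size of the effect it reports "a Mantel-Haenszel estimator of the common risk difference and its two-sided 95% confidence interval". One SAS statement supplies both: "tables BaselineIGA *Treatment*Response/riskdiff(common) cmh". SAP 6.6 sets the level: "The two-sided significance level is 5% with a two-sided 95% confidence interval". SAP 9.1 also asks for a Clopper-Pearson interval for the success rate in each arm.

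The method is carried forward. SAP 9.1.1 applies it to the three sensitivity analyses. SAP 9.2.1 states: "Incidence of success in IGA at Week 1 and Week 8 (as well as Week 2 and Week 6) will be analyzed" in the manner of 9.1. SAP 9.5 states: "Incidence of success in IGA will also be analyzed in the following subgroups in the same manner as described in" Section 9.1, and lists baseline IGA 2 and 3 among the subgroups.

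The SAP does not give a variance estimator or limit formula for the difference, a rule for tables with no responders, or a statement of how to read a case where the interval and the test disagree.

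**The concern.** The CMH statistic uses a variance computed under no difference. The usual interval around a Mantel-Haenszel risk difference uses a variance computed at the observed rates and is symmetric. The two agree closely when responders are plentiful and drift apart when they are few. Few are planned for: at the planning vehicle rate, 60 × 0.0270 = 1.6 responders are expected.

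Two things are at stake. First, a published interval may exclude zero beside a p-value just above 0.05, most likely for the 0.3% arm. Second, the interval may cover less often than its label says wherever success is rarer than at Week 4. The mild subgroup is the obvious candidate: success needs a 2-grade improvement, so a subject starting at IGA 2 must reach IGA 0.

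**Working it through.** **Inputs.** The planning rates are from SAP 12.2: "the primary variable of incidence of success in IGA was 20.93% in the 1% OPA-15406 group and 2.70% in the vehicle group, respectively". The 0.3% arm's rate is from Protocol 1.2.2.4: "the incidence of success in IGA was 14.63%, 20.93%, and 2.70% in the 0.3% OPA-15406 group, the 1% OPA-15406 group, and the vehicle group". There are 60 per arm, and missing IGA counts as non-response (SAP 6.3.1), so treated subjects stay in the denominator. The level is 5% two-sided. My assumptions are the Wald-type limits, every rate at other visits or in subgroups, and every mild/moderate split.

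**The plan's own figure.** For 20.93% against 2.70%, exact power of the two-sided Fisher test is 79.1% at 53 per group and 80.2% at 54. The plan's 54 is reproduced.

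**One table by hand: 6/60 against 1/60, one stratum.**
- Difference: 0.1000 − 0.0167 = 0.0833.
- SE = √(0.1 × 0.9/60 + 0.01667 × 0.98333/60) = √(0.001500 + 0.000273) = 0.0421.
- Interval: 0.0833 ± 1.96 × 0.0421 = 0.08% to 16.6%. It excludes zero.
- CMH: (6 − 3.5)² ÷ [60 × 60 × 7 × 113/(120² × 119)] = 6.25/1.662 = 3.76, p = 0.0525. Not significant.

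A two-stratum case behaves the same way: 3/30 and 3/30 on active against 0/30 and 1/30 on vehicle gives 0.08% to 16.6% with p = 0.053.

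**How often they disagree** (all outcomes enumerated, one stratum, 60 per arm). About 1% of trials at 20.93% against 2.70%, and 3.6% at 14.63% against 2.70%. With two strata the figures are 0.65% to 0.8% and 2.1% to 2.9%, depending on the assumed stratum split and rates. At the planning rates in one stratum, every disagreement is an interval that excludes zero beside a non-significant test. With equal true rates of 5% or 10%, the interval excludes zero in 6.0% of trials, against 4.6% and 5.0% for CMH.

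**Coverage of the Wald-type interval** (one stratum; 0/0 means no responder in either arm):

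| Per arm | Active vs vehicle | Source of rates | Coverage | P(0/0) |
|---|---|---|---|---|
| 60 | 20.93% vs 2.70% | planning | 94.0% | under 0.1% |
| 60 | 14.63% vs 2.70% | foreign trial | 94.7% | under 0.1% |
| 60 | 2% vs 0.5% | assumed | 77% | 22% |
| 60 | 3% vs 1% | assumed | 83% | 9% |
| 60 | 5% vs 1% | assumed | 93% | 3% |
| 60 | 2% vs 2% | assumed | 98% | 9% |
| 30 | 5% vs 1% | assumed | 78% | 16% |
| 30 | 10% vs 1% | assumed | 95% | 3% |

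P(0/0) is [(1 − p₁)(1 − p₀)]ⁿ; for example (0.95 × 0.99)³⁰ = 0.159. In that table the interval is [0, 0] and misses any non-zero difference. At 5% against 1% with 30 per arm this accounts for 0.159/0.217 = 73% of the misses; at 3% against 1% with 60 it is 0.088/0.166 = 53%.

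**Why a score interval agrees with CMH.** Take weights w = n₁n₀/N in each stratum and let m be the stratum's responders. At zero difference the weighted difference is w(x₁/n₁ − x₀/n₀) = x₁ − n₁m/N, which is the CMH numerator. The score variance with the N/(N − 1) factor is w² × [m(N − m)/N²] × [N/(n₁n₀)] × N/(N − 1) = n₁n₀m(N − m)/[N²(N − 1)], which is the CMH variance. Summed over strata, the two statistics are the same. In one stratum of 60 against 60, the interval and the test agreed on all 61 × 61 tables.

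**The case against.** The case for leaving the plan alone is substantial, and most of it stands.

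- **The primary decision is untouched.** SAP 6.6.1 and 9.1 make the CMH test the only gate, and Week 4 coverage is close to nominal. A reader might infer that the primary result is unreliable. The documents do not support that.
- **The contradictions are marginal.** In one stratum of 60 per arm, every table where they conflict has p between 0.050 and 0.0543.
- **The low-rate scenarios are assumptions.** A reader might infer that coverage is far below 95% at the rates expected at Week 1 and in mild subjects. No such rates are stated, nor is a mild/moderate split. The deep shortfall appears only when events are very rare. It largely disappears at 5% against 1% with 60 per arm or 10% against 1% with 30, and it does not arise with equal rates of 2%.
- **The zero-width case is partly covered.** The per-arm Clopper-Pearson limits still show uncertainty: for 0/30 the upper limit is 1 − 0.025^(1/30) = 11.6%, and for 0/60 it is 6.0%.
- **The other intervals are secondary.** SAP 6.6.1 treats p-values outside the primary analysis as reference only.

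What the objection does not remove is that, under the assumed form, the planned code would print a zero-width 95% interval for the difference beside per-arm limits that reach 11.6%. A test and interval that can conflict would also be reported side by side with no rule for reading them, when a matched pair is available.

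**Conclusion.** The point holds as a minor one, worth making because it is cheap. It rests on the assumption that `riskdiff(common)` yields symmetric Wald-type limits; the SAP does not say so. At Week 4 the effect is small: coverage of 94.0% to 94.7%, and disagreement with CMH of about 1% (1% arm) and 2% to 4% (0.3% arm). At the other visits and in the mild subgroup the effect depends on rates that the documents do not give. It ranges from negligible to a shortfall of 17 to 18 points when active success is about 2% with 60 per arm (95 − 77 = 18) or about 5% with 30 per arm (95 − 78 = 17). Nothing here invalidates the primary analysis or its gatekeeping.

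**What to change.** In SAP 9.1, 9.1.1, 9.2.1 and 9.5, keep the Mantel-Haenszel point estimate and the per-arm Clopper-Pearson intervals. For the difference, report the stratified Miettinen-Nurminen score interval, stating Mantel-Haenszel stratum weights and the per-stratum N/(N − 1) factor, since agreement with CMH depends on both. Its one-stratum coverage is 94.4% at 20.93% against 2.70% and 97.8% at 3% against 1% with 60 per arm, and 98.8% at 5% against 1% with 30. It does not collapse when neither arm has a responder.

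If the present interval is kept, name its variance formula, add a rule for tables with no responders, and state that the CMH test governs if the two disagree.

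The cost is SAP wording and one program option or macro, checked to use these weights and this factor. Intervals will be wider and conservative when events are very rare.
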